CQMP	Clinical Quality Management Plan
CRF	Case Report Form
CROMS	Clinical Research Operations and Management Support
DAIDS	Division of AIDS
DHHS	Department of Health and Human Services
DMID	Division of Microbiology and Infectious Diseases, NIAID, NIH, DHHS
eCRF	Electronic Case Report Form
FDA	Food and Drug Administration
FWA	Federalwide Assurance
GCP	Good Clinical Practice
GI	Gastrointestinal
IB	Investigator's Brochure
ICF	Informed Consent Form
ICH	International Conference on Harmonisation
IEC	Independent or Institutional Ethics Committee
IND	Investigational New Drug Application
IRB	Institutional Review Board
ISM	Independent Safety Monitor
KG	Kilogram
MG	Milligram
mL	Milliliter
MOP	Manual of Procedures
NIAID	National Institute of Allergy and Infectious Diseases, NIH, DHHS
NIH	National Institutes of Health
OHRP	Office for Human Research Protections
PCR	Polymerase Chain Reaction
PD	Pharmacodynamic
PHI	Protected Health Information
PI	Principal Investigator
PK	Pharmacokinetics

PRBC	Packed Red Blood Cell
QA	Quality Assurance
QC	Quality Control
SAE	Serious Adverse Event/Serious Adverse Experience
SOP	Standard Operating Procedure
US	United States

PROTOCOL SUMMARY

Title:	Evaluation of the Pharmacokinetics and Pharmacodynamics of Ganciclovir in Premature Infants Receiving Treatment for Cytomegalovirus Infection
Phase:	Not Applicable (clinical sampling study)
Population:	Male and female premature infants < 32 weeks gestation who are being treated for medical reasons with intravenous ganciclovir for proven [e.g., culture- or polymerase chain reaction (PCR)-confirmed] CMV infections. Subjects will be stratified according to age (gestational and chronologic)
Sample Size:	32
Number of Sites:	15
Study Duration:	5 years
Subject Participation Duration:	Up to 7 weeks
Description of Agent or Intervention:	None. This is not an interventional study. It is a clinical sampling study, and ganciclovir will not be administered as part of the protocol.
Objectives:	The goals of the study are to determine ganciclovir pharmacokinetic and pharmacodynamic parameters in premature infants who receive IV ganciclovir as part of medical care to treat CMV infections.
	Primary:
	
• To define the pharmacokinetics of ganciclovir in premature (< 32 weeks gestational age at birth) infants
	Secondary:

- To assess changes in quantitative viral DNA in whole blood as a function of ganciclovir pharmacokinetics
- To assess clearance of CMV in urine as a function of ganciclovir pharmacokinetics

Exploratory:

- To assess development of neutropenia as a function of ganciclovir pharmacokinetics
- To determine the potential for the development of resistance to ganciclovir as a function of pharmacokinetics, dose, age, and duration of therapy

Outcome Measures

Primary Endpoint:

- Plasma pharmacokinetics parameters for ganciclovir AUC₁₂

Secondary Endpoints:

- Plasma pharmacokinetics parameters for ganciclovir, including maximum serum concentration (C_{max}), half-life (T_{1/2}), CL, and V_d
- Correlation of ganciclovir plasma concentrations with CMV whole blood viral load
- Correlation of ganciclovir plasma concentrations with clearance of CMV in urine

Exploratory Endpoints:

- Correlation of ganciclovir plasma concentrations with neutropenia
- Detection of resistance to ganciclovir

Description of Study Design:

This is an open-label, multi-center, clinical sampling study to assess ganciclovir pharmacokinetics and pharmacodynamics in premature infants undergoing antiviral therapy for CMV. Only those subjects who receive ganciclovir for clinical reasons will be enrolled. The decision to initiate ganciclovir therapy will be

made by the attending physician based upon his/her clinical decision to treat virologically-confirmed CMV infection; infants receiving such therapy and meeting entry criteria will then be eligible for this study. Therefore, ganciclovir will not be provided under this protocol.

Subjects meeting enrollment criteria will be entered into this clinical trial. Following enrollment, subjects will be stratified by gestational age and by chronologic age as follows: 1) \leq 27 weeks 6 days gestational age at birth and \leq 30 days chronologic age at study enrollment; 2) \leq 27 weeks 6 days gestational age at birth and $>$ 30 days chronologic age at study enrollment; 3) \geq 28 weeks 0 days gestational age at birth and \leq 30 days chronologic age at study enrollment; 4) \geq 28 weeks 0 days gestational age at birth and $>$ 30 days chronologic age at study enrollment. The total sample size across these four cohorts is 32 subjects. Subjects in each cohort with inadequate pharmacokinetic data for analysis (e.g., due to dropping out of the study before PK assessments are performed, or blood sampling obtained but is inadequate for analysis) may be replaced and will not count toward the total of 32 subjects. Additionally, enrollment of an additional 2-3 subjects may be allowed for operational reasons.

A full pharmacokinetic profile will be obtained following at least one of the ganciclovir doses received after study enrollment. The PK samples will be obtained after the subject has received study assessment dose 3, 4, 5, 6, 7, or 8 of intravenous ganciclovir. Typically, ganciclovir is administered twice per day in these infants for a duration in excess of 10 days. Specimens will be shipped for processing at that time. The pharmacokinetic data will then be provided to the study site, including the AUC and CL values for information purposes.

[figure not shown]
Dose and duration of intravenous ganciclovir therapy is at the discretion of the treating physician and will not be dictated by the research protocol. Both whole blood for CMV PCR and urine for CMV detection will be obtained once in each study period as long as the subject is receiving intravenous ganciclovir therapy. These specimens will be used to determine viral load and ganciclovir resistance. Since ganciclovir is a renally

excreted drug, serum creatinine will be drawn for the research protocol on the day that the ganciclovir pharmacokinetic specimens are obtained in order to calculate creatinine clearance using a method such as the modified Schwartz formula, and thus correlate ganciclovir clearance with renal function. Otherwise, data from hematology assessments (WBC count and differential, hemoglobin, platelet count) and from chemistry labs (serum creatinine, AST, and ALT) will be recorded on the study case report forms during each study period if they are being obtained for clinical reasons, but will not be drawn only for the purposes of the study. Ganciclovir dosing information (mg/dose, dosing interval, and subject weight) will be recorded on the day of the pharmacokinetic blood draws, and weekly from Period 1 through Period 7 as long as the subject is receiving intravenous ganciclovir therapy.

If the subject continues to receive intravenous ganciclovir from Study Assessment Day 18 through Study Assessment Day 24 (Period 4), a second PK assessment may be performed at the request of the treating physician if the subject weighs 575 grams or more at the time of specimen collection.

Estimated Time to Complete Enrollment: 4 years from enrollment of the first study subject

2 BACKGROUND INFORMATION AND SCIENTIFIC RATIONALE

2.1 Background Information

The natural history of congenitally acquired CMV infection is well described.¹⁻⁷ In contrast, outcomes of perinatally and postnatally acquired CMV infections are less well characterized. It is generally agreed that postnatal acquisition of CMV in term infants does not lead to symptomatology or disease.⁸ In preterm infants, initial case reports suggested that peri- and postnatally acquired CMV infections could produce severe disease.⁹⁻¹⁴ Larger series and case-controlled trials more recently suggest that symptomatic disease in preterm babies is less common than asymptomatic infection, and long-term sequelae are rare.¹⁵⁻¹⁹ Nevertheless, severe disseminated CMV disease can occur in premature infants, including life-threatening pneumonitis, hepatitis, and thrombocytopenia.²⁰ Antiviral therapy in such patients is frequently used, albeit without either controlled data to demonstrate benefit or knowledge of proper dosing regimens.¹² In patients with symptomatic congenital CMV disease, six weeks of intravenous ganciclovir improves hearing outcomes in early childhood,²¹ and may benefit neurodevelopmental outcomes as well.²² In premature babies with visceral disease from postnatally acquired CMV, the goal of antiviral therapy is different; namely, it is to treat the end-organ disease, which is occurring at that time, rather than to prevent or improve long-term sequelae. Without efficacy data, the duration of treatment is variable, but anecdotal experience suggests that it generally is in the range of two to four weeks of total antiviral therapy. Approximately two-thirds of treated neonates receiving six weeks of intravenous ganciclovir develop Grade 3 or 4 neutropenia (utilizing the DAIDS Toxicity Tables) during therapy.²¹

The appropriate dose of intravenous ganciclovir for premature babies has not been studied. Previous studies of ganciclovir have indicated that the area-under-the-concentration curve (AUC) of ganciclovir is most closely related to virologic treatment success.²³ Data from an National Institute of Allergy and Infectious Diseases (NIAID) CASG Phase II study of intravenous ganciclovir (6 mg/kg/dose q 12 hrs) in term neonates with symptomatic congenital CMV disease revealed a median AUC₁₂ of 27 μ gxh/mL (mean AUC₁₂=32.3+13.7 μ gxh/mL, range 17.2 to 55.9 μ gxh/mL, n=13).²⁴ A more recent CASG investigation of oral valganciclovir included comparative pharmacokinetic data following 6 mg/kg/dose every 12 hrs of intravenous ganciclovir. The mean AUC₁₂ in young neonates (median age: 16.5 days) on the second day following study enrollment was 38.2 μ gxh/mL (median: 25.5 μ gxh/mL), but the coefficient of variation was large (112).²⁵ In five neonates in whom pharmacokinetic sampling was performed on day 4 and day 34 of intravenous ganciclovir therapy, ganciclovir clearance nearly doubled and AUC₁₂ reduced by almost half over the 30 day interval,²⁵ suggesting that maturational changes may be occurring rapidly in early life which may affect ganciclovir dosing. No data exist on ganciclovir dosing in very premature babies, who are at greatest risk for CMV disease.

due to the absence of transplacental antibodies. Notably, acyclovir must be dose-adjusted based upon renal function such as that which can occur with prematurity.²⁶

The CASG and the UAB Central Unit have had significant success in performing multi-center pharmacokinetic and pharmacodynamic studies with both ganciclovir and valganciclovir in infants during the first month of life.^{21,22,25,27-30} In this study, this experience will be utilized to further define the utility of this drug in very premature children.

2.2 Rationale

Parenteral ganciclovir is used regularly in premature neonates to treat end-organ disease, but the appropriate dose to use has never been studied or defined. This is a clinical sampling study, and premature infants who receive intravenous ganciclovir as part of clinical care will be eligible for participation. A prospective treatment trial is not feasible at this time, but this study will inform dosing parameters for a subsequent prospective study to evaluate dose and effectiveness. At the completion of the study, appropriate dosing of intravenous ganciclovir in premature infants will be defined. While this will not allow for conclusions to be drawn regarding efficacy, these data will help minimize toxicity for future premature babies treated with ganciclovir. Importantly, all pharmacokinetic assays will be performed in the UAB Antiviral Pharmacology Laboratory. Of relevance to this trial, this laboratory has developed the methodology to process microspecimens of blood for ganciclovir drug concentrations.

2.3 Potential Risks and Benefits

2.3.1 Potential Risks

As a sampling study, the potential risks relate to blood draws (e.g., bruising at the site, infection, anemia possibly requiring packed red blood cell transfusion). Requiring a baby to be at least 500 grams at the time of study enrollment will ensure that blood volumes withdrawn will be acceptable by research standards. Additionally, virtually all of the subjects will have long-term intravenous access for clinical care, through which blood can be withdrawn without risk of discomfort from the needle stick or bruising at the site during or after the blood drawing and rarely an infection. Transfusions are expected in hospitalized premature infants. One study reported that extremely premature neonates receive an average of 5.2 ± 4.2 transfusions over a six week period.³¹ Other trials have reported similar numbers of transfusions in this population.^{32,33} It is possible that even higher numbers of transfusions might be experienced in the at-risk population in this sampling study since they are receiving the myelosuppressive drug ganciclovir as part of clinical care. Transfusions are not associated with long-term sequelae.³³ Nevertheless, throughout the conduct of this study, transfusion rates will be carefully monitored.

2.3.2 Known Potential Benefits

Knowledge of a given subject's pharmacokinetic profile may allow for rational clinical adjustments in treatment dose, thereby minimizing potential drug toxicity and maximizing potential antiviral efficacy.

3 OBJECTIVES

3.1 Study Objectives

Primary:

- To define the pharmacokinetics of ganciclovir in premature (< 32 weeks gestational age at birth) infants

Secondary:

- To assess changes in quantitative viral DNA in whole blood as a function of ganciclovir pharmacokinetics
- To assess clearance of CMV in urine as a function of ganciclovir pharmacokinetics

Exploratory:

- To assess development of neutropenia as a function of ganciclovir pharmacokinetics
- To determine the potential for the development of resistance to ganciclovir as a function of pharmacokinetics, dose, age, and duration of therapy

3.2 Study Outcome Measures

3.2.1 Primary Outcome Measures

Primary Endpoint:

- Plasma pharmacokinetics parameters for ganciclovir AUC12

3.2.2 Secondary Outcome Measures

Secondary Endpoints:

- Plasma pharmacokinetics parameters for ganciclovir, including maximum serum concentration (Cmax), half-life (T1/2), CL, and Vd
- Correlation of ganciclovir plasma concentrations with CMV whole blood viral load
- Correlation of ganciclovir plasma concentrations with clearance of CMV in urine

3.2.3 Exploratory Outcome Measures

Exploratory Endpoints:

- Correlation of ganciclovir plasma concentrations with neutropenia
- Detection of resistance to ganciclovir

4 STUDY DESIGN

This is an open-label, multi-center, clinical sampling study of ganciclovir pharmacokinetics and pharmacodynamics of ganciclovir in premature infants undergoing antiviral therapy for CMV. Only those subjects who receive ganciclovir for clinical reasons will be enrolled. The decision to initiate ganciclovir therapy will be made by the attending physician based upon his/her clinical decision to treat virologically-confirmed CMV infection; infants receiving such therapy and meeting entry criteria will then be eligible for this study. Therefore, ganciclovir will be dispensed from the institution's pharmacy and not provided under this protocol.

Subjects meeting enrollment criteria will be entered into this clinical trial. Following enrollment, subjects will be stratified by gestational age and by chronologic age as follows: 1) \leq 27 weeks 6 days gestational age at birth and \leq 30 days chronologic age at study enrollment; 2) \leq 27 weeks 6 days gestational age at birth and $>$ 30 days chronologic age at study enrollment; 3) \geq 28 weeks 0 days gestational age at birth and \leq 30 days chronologic age at study enrollment; 4) \geq 28 weeks 0 days gestational age at birth and $>$ 30 days chronologic age at study enrollment. The total sample size across these four cohorts is 32 subjects. Subjects in each cohort with inadequate pharmacokinetic data for analysis (e.g., due to dropping out of the study before PK assessments are performed, or blood sampling obtained but is inadequate for analysis) may be replaced and will not count toward the total of 32 subjects. Additionally, enrollment of an additional 2-3 subjects may be allowed for operational reasons.

Treatment Day 1 is the calendar day when the first dose of intravenous ganciclovir was administered to the study subject for clinical care, and Treatment Dose 1 corresponds to the first dose of intravenous ganciclovir the patient receives under clinical care. Study Assessment Dose 1 is the first dose of intravenous ganciclovir the subject receives following enrollment on the trial, and Study Assessment Day 1 is the calendar day when Study Assessment Dose 1 is administered. Both Treatment Day 1 and Treatment Dose 1 can coincide with or precede study enrollment; Study Assessment Day 1 and Study Assessment Dose 1 by definition will follow study enrollment, and may or may not equate with Treatment Day 1 and Treatment Dose 1. Typically, ganciclovir is administered twice per day in these infants.

With the receipt of one of the Study Assessment Doses (dose 3, 4, 5, 6, 7, or 8) of intravenous ganciclovir, pharmacokinetic specimens will be obtained at 0h (immediately prior to IV ganciclovir dose; window: -15 min), 1h (immediately after the end of the IV ganciclovir dose; window: +15 min), 2-3h, 5-7h, and 10-12h. This complete set of pharmacokinetic time points will allow for the AUC and clearance (CL) to be calculated in each subject. Specimens will be shipped to the UAB Antiviral Pharmacology Laboratory for processing at that time. The pharmacokinetic data will then be provided to the study site, including the AUC and CL values,

for information purposes. The decision of whether or not to adjust the dose will be a clinical one to be decided by the treating physician, and will not be dictated by the research protocol. The parameters for AUC and CL from prior CASG ganciclovir^{27,30} and valganciclovir^{25,29} studies demonstrate that these PK parameters may be useful in guiding dose adjustments. Duration and dose of intravenous ganciclovir therapy is made at the discretion of the treating physician and will not be dictated by the research protocol.

Both whole blood for CMV PCR and urine for CMV assessment will be obtained serially through Study Assessment Period 7 as long as the subject is receiving intravenous ganciclovir therapy (that is, until the ganciclovir is permanently discontinued). These specimens will be used to determine viral load and, as indicated, ganciclovir resistance. At each sample collection time, urine will be split into two aliquots. These aliquots will be available for CMV detection as appropriate, based upon whole blood viral loads. Specimens will then be available for subsequent testing for ganciclovir resistance in the UAB Virology Resistance Laboratory. Since ganciclovir is a renally excreted drug, serum creatinine will be drawn for the research protocol on the day that the ganciclovir pharmacokinetic specimens are obtained in order to calculate creatinine clearance using a method such as the modified Schwartz formula, and thus correlate ganciclovir clearance with renal function. Otherwise, data from hematology assessments (WBC count and differential, hemoglobin, platelet count) and from chemistry labs (serum creatinine, ALT, and AST) will be recorded on the study case report forms each study assessment period if they are being obtained for clinical reasons, but will not be drawn only for the purposes of the study. Ganciclovir dosing information (mg/dose, dosing interval, and subject weight) will be recorded on the day of the pharmacokinetic blood draws. Once a subject is successfully enrolled into the study the ganciclovir dosing information (mg/dose and dosing interval) will be recorded from the start of clinical treatment of ganciclovir until date of enrollment. After enrollment ganciclovir dosing information (mg/dose and dosing interval) will be captured from Study Assessment Period 1 through the Study Assessment Period 7; as long as the subject is receiving intravenous ganciclovir therapy.

If the subject continues to receive intravenous ganciclovir from Study Assessment Day 18 through Study Assessment Day 24 (Period 4), and at the request of the treating physician, an additional set of blood samples will be obtained for PK assessments if the subject is 575 grams or more at time of collection. The additional samples will be analyzed as they are received in the UAB Antiviral Pharmacology Laboratory and the results will be provided to the treating physician for information purposes. Specimens would be obtained around one dose administered during this window, using the same sampling times as with the first pharmacokinetic draws.

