5 STUDY ENROLLMENT AND WITHDRAWAL

Male and female premature infants < 32 weeks gestation of any ethnicity who are being treated with intravenous ganciclovir for proven [e.g., culture- or polymerase chain reaction (PCR)-confirmed] CMV infections are eligible for enrollment. Participating clinical sites will identify potential study subjects. Patients meeting study eligibility criteria may be offered enrollment into the trial. Informed consent signed by study subject's parent(s) or guardian(s) must be obtained prior to study enrollment. Site investigators are all clinicians and also care providers for the neonatologists at their respective institutions, and therefore have direct access to the study population. The study population will be drawn from the in-hospital setting. Potential subjects will be identified by the site investigators and the study coordinators.

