5.1 Subject Inclusion Criteria

1. Signed informed consent from parent(s) or legal guardian(s)
2. Confirmation of CMV infection from urine, blood, or saliva by culture, shell vial, or PCR tests (local lab)
3. Receiving intravenous ganciclovir, prescribed by the patient's physician and anticipated to receive at least 3 more doses after consenting
4. < 32 weeks gestational age at birth
5. ≥ 500 grams at study enrollment

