11 STATISTICAL CONSIDERATIONS

11.1 Study Hypotheses

Our primary hypothesis is that ganciclovir pharmacokinetics and pharmacodynamics in premature infants with postnatally or congenitally acquired CMV infection differ from those in term neonates and older infants.

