11.2 Sample Size Considerations

The primary outcome used for power analysis is the area under the curve for 12 hours (AUC12) following 6 mg/kg of ganciclovir. In a one-way ANOVA design, we would like to compare the means of 4 groups (see below) with sample sizes of approximately 8, 8, 8, and 8 (32 total subjects enrolled across the four cohorts). If the means of the AUC12 of the 4 groups are 20, 20, 30, and 35 assuming a common standard deviation of 10, these mean differences (equivalent to an effect size of 0.72) will be detected at 83% power using an F test with 0.05 level of significance. In order to look at other possible scenarios, we provide the table below that looks at other standard deviation values, its corresponding effect size given the differences in means as described above, and the power of detecting such a difference/effect size. If estimating the AUC without regard to the groups, the margin of errors associated with a 95% confidence interval assuming different standard deviation values and a sample size of 32 are given in the table below.

Standard Deviation	S=8	S=9	S=10	S=11
Effect Size	0.81	0.72	0.64	0.59
Power	96%	91%	83%	75%
Margin of Error	2.33	2.62	2.91	3.20

The above parameter values were hypothesized based on results from other studies.^{25,34} It is worth noting that there are no PK data in this population and the results are likely to be different from other studies due to the maturational changes.

Following enrollment, subjects will be stratified by gestational age and by chronologic age as follows: 1) \leq 27 weeks 6 days gestational age at birth and \leq 30 days chronologic age at study enrollment; 2) \leq 27 weeks 6 days gestational age at birth and $>$ 30 days chronologic age at study enrollment; 3) \geq 28 weeks 0 days gestational age at birth and \leq 30 days chronologic age at study enrollment; 4) \geq 28 weeks 0 days gestational age at birth and $>$ 30 days chronologic age at study enrollment. The total sample size across these four cohorts is 32 subjects. Enrollment of an additional 2-3 subjects may be allowed for operational reasons. If the 32

subjects enrolled are not balanced across the 4 groups, we instead will look at the correlation between gestational age at birth. With 32 subjects, the margin of errors of a 95% confidence interval for estimating the correlation given the observed correlation values are given below.

Correlation	0.4	0.5	0.6	0.7
Margin of Error	0.6	0.542	0.47	0.38

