11.4 Final Analysis Plan

Primary analysis: To compare the ganciclovir pharmacokinetics and pharmacodynamics as measured by AUC₁₂ in premature infants with postnatally or congenitally acquired CMV infection differ from those in term neonates and older infants, we will construct 95% confidence intervals around the mean AUC₁₂ for the subjects in this study and compare these means across the groups. If there are not enough subjects in the groups, we will use the actual gestational age and correlate it with the AUC₁₂ by computing correlation coefficients and a fitting regression model. Additional pharmacokinetic parameters that compose analyses for secondary endpoints include Cmax, T1/2, CL, and VD. For measures that are repeated over time, we will utilize mixed models for repeated measures. In addition to being able to compare these outcomes for the different groups, we can also look into how these measures change over time and adjust for covariates.

Ganciclovir pharmacokinetic parameters will initially be determined using non-compartmental analysis (WinNonlin v5.3) for each individual subject. The parameters (AUC₁₂, CL, Vd, etc.) will be summarized and further used for exploratory pharmacodynamic analysis. We will also apply pharmacokinetic models to the concentration-time data, either individually or using a population approach. We may also pool these data with prior CASG 109 PK data in order to have a more robust covariate analysis across a wider range of ages.

The second pharmacokinetic analysis will utilize either population pharmacokinetic or individual modeling approaches, depending upon how much data we actually are able to collect and the nature of those data. Concentration-time data will be analyzed using nonlinear mixed-effects in ADAPT 5.0. If a population approach is employed, this will give us the opportunity to explore

relationships between ganciclovir exposure and multiple covariates, such as gestational age, weight, renal function, etc.

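### The older cohorts have no upper age limit, and neither the cohort means nor the gestational-age-only fallback models maturation after birth

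*Protocol*

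**What the plan says.** **Eligibility.** Protocol 5.1 admits infants "< 32 weeks gestational age at birth" who weigh "≥ 500 grams at study enrollment". None of the five inclusion or five exclusion criteria sets a maximum chronologic age, postmenstrual age or weight. The practical limits are continuing clinical IV ganciclovir and hospital stay: "The study population will be drawn from the in-hospital setting".

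**Cohorts.** Protocol section 4 crosses gestational age at birth (up to 27w6d, or 28w0d and above) with chronologic age at enrolment (up to 30 days, or more than 30 days). Cohorts 2 and 4 start at day 31 and have no end; cohort 4, for instance, is defined as births at or after 28 "weeks 0 days gestational age at birth and $>$ 30 days chronologic age at study enrollment". The SAP repeats these definitions in Appendix B and in Appendix C, item 3.3.4. The SAP closes a group at 8 infants. The protocol fixes only the total of 32, with about 8 per group.

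**Maturation.** Protocol 2.1 reports that in five neonates sampled on days 4 and 34 of therapy, clearance nearly doubled and AUC12 fell by almost half, "suggesting that maturational changes may be occurring rapidly in early life which may affect ganciclovir dosing".

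**Analysis.** Protocol 11.4 puts 95% confidence intervals around mean AUC12 and will "compare these means across the groups". If groups are too small (11.4) or unbalanced (11.2), it turns to gestational age at birth and its correlation or regression with AUC12. SAP Appendix B uses mixed models for the group comparison and gives no fallback. In both documents covariate adjustment is a possibility. The population model is conditional, and the covariates named for it are gestational age, weight and renal function, with an open-ended *etc.* Neither chronologic nor postmenstrual age is named.

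**The concern.** The primary hypothesis in Protocol 11.1 is that the pharmacokinetics of these infants "differ from those in term neonates and older infants", and the background gives rapid maturation as a reason to expect this. Maturity at sampling depends on gestational age at birth and on time since birth. The plan treats time since birth only as a cut at 30 days, and the fallback drops even that cut.

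Two things are at stake. A cohort mean taken over infants several weeks apart in maturity does not say which infants it describes. And if recruitment is uneven, so that the fallback becomes the primary analysis, the study would have no prespecified way to see the post-birth maturation that its own background reports.

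**Working it through.** **1. The plan's own power figure.** Inputs from Protocol 11.2: means 20, 20, 30, 35; SD 10; 8 per group; alpha 0.05. The grand mean is 26.25 and the squared deviations sum to 168.75. So f = √(168.75/4)/10 = 0.65 and λ = 32 × 0.65² ≈ 13.5. With 3 and 28 degrees of freedom the F test has 83.1% power, which reproduces the stated 83%.

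**2. Spread of maturity within a cohort.** Postmenstrual age = gestational age at birth + chronologic age.
- Cohort 4 at day 31: 28w0d gives 196 + 31 = 227 d (32w3d); 31w6d gives 223 + 31 = 254 d (36w2d).
- Cohort 4 upper end: 223 + 60 = 283 d (40w3d) if enrolment runs to day 60, or 223 + 90 = 313 d (44w5d) to day 90.
- Possible span: 283 − 227 = 56 d (8 weeks), or 313 − 227 = 86 d (about 12 weeks).

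Days 60 and 90 are assumptions, because the documents give no distribution of age at enrolment.

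**3. The protocol's rate of change.** A doubling in 30 days is ln 2 × 7/30 = 0.16 on the log scale, about 16% per week. It comes from five neonates, so the simulation below uses smaller slopes of 4–8% per week.

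**4. What each analysis can detect.** Simulation, 8,000 trials per setting, 8 infants per cohort. Gestational age is uniform on 23–27.9 or 28–31.9 weeks. Chronologic age is uniform on 3–30 days, or on day 31 to the stated maximum. Residual SD of log AUC12 is 0.4. All of these are assumptions. Entries are the percentage of trials significant at 0.05, for slopes of 4% to 8% per week.

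| What drives log AUC12 | Oldest age | Four-cohort F test | Gestational age only (fallback) | Postmenstrual age only | Gestational + chronologic age |
|---|---|---|---|---|---|
| Both, equal slopes | 60 d | 24–73 | 28–73 | 48–96 | 37–92 |
| Both, equal slopes | 90 d | 35–89 | 25–62 | 68–99+ | 56–99 |
| Chronologic age only | 60 d | 13–40 | 4–5 | 14–38 | 19–62 |
| Chronologic age only | 90 d | 25–75 | 3–4 | 36–86 | 40–94 |
| Gestational age only | 60 d | 14–46 | 29–79 | 17–50 | 22–69 |
| Gestational age only | 90 d | 15–48 | 29–81 | 12–31 | 22–69 |

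The two-variable regression beats the F test in every row. It does not beat a one-variable model that happens to be the true one. The fallback has no power when age since birth is the driver.

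**5. If the truth is pure cohort steps.** With the planning means and SD 10, the F test has 83%, the two-variable regression 71–74%, and postmenstrual age alone 49–68% when the means are taken in the order listed. Protocol 11.2 does not say which mean belongs to which cohort. With the steps placed mainly along chronologic age instead, the two-variable regression is still at 71–74%, while the fallback falls from about 81% to about 5%.

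**The case against.** **Infants at term-equivalent age.** A reader might infer that such infants could fill half the trial and contaminate it. The documents do not support this. Protocol 3.1 defines the target population by gestational age at birth, so an infant born before 32 weeks belongs to it at any later age, and having about half the infants beyond 30 days is part of the design. Under the spreads in step 4, the share at or above 37 weeks is 37% of cohort 4 and none of cohort 2 to day 60, about 3 of 32. To day 90 it is about 69% and 17%, so 5.5 + 1.4, or about 7 of 32 (22%). For all 16 to qualify, an infant born at 24w0d could enrol no earlier than day 91 (259 − 168).

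**Power and age.** A reader might also infer that the missing age limit weakens the cohort comparison. When age since birth plays a part, the F test gains power as the range extends, because the contrast widens.

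**Postmenstrual age as a replacement.** It would be tempting to let postmenstrual age replace the cohorts. It forces the same weekly slope on gestational age and on age since birth. If gestational age alone drives clearance at 12% per week and ages run to day 90, it has about 54% power against about 80% for the F test. Overlap in postmenstrual age between cohorts follows from crossing two factors and is not an error. No section makes 37 weeks a pharmacokinetic boundary, so a split there is not required.

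**Existing provisions.** The plan measures creatinine on the PK day to relate clearance to renal function, allows covariate adjustment, and may pool earlier data across a wider age range. A second profile in Period 4 could show change within an infant. These provisions stand, but they are optional, conditional or taken only at the treating physician's request, apart from the creatinine measurement. None commits to age since birth.

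**Conclusion.** The point holds as a gap in the analysis. Nothing caps age at enrolment, maturity can vary by several weeks within a cohort, and the only prespecified fallback uses gestational age alone. That fallback rejects in about 3–5% of simulated trials when age since birth drives AUC12, which is no better than its false-positive rate.

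The gap matters most if recruitment is uneven. If the SAP's cap of 8 per group is enforced and every group fills, the fallback would not be needed, and what remains is that cohort means describe maturity only coarsely.

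The size rests on assumed age spreads, slopes and residual SD. The near-doubling of clearance comes from five neonates, and extending it to older preterm infants is an extrapolation. The finding supports a low-cost improvement. It does not show that the eligibility criteria or the cohorts are wrong.

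**What to change.** In Protocol 11.4 (with matching wording in 11.2) and SAP Appendix B:

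- Keep the four-cohort comparison.
- Prespecify a regression of log AUC12 and of CL on gestational age at birth and chronologic age on the PK day, both continuous. CL belongs here because doses are set clinically, so AUC12 also reflects the dose given.
- Use this regression in place of the gestational-age-only fallback when the cohorts are unbalanced.
- Add a supportive model with postmenstrual age, the sum of the two, which tests whether one slope is enough.
- Describe the distribution of postmenstrual age at PK in each cohort.

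Gestational age and date of birth are already recorded, so no new procedure, blood sample or enrolment rule is needed. The cost is one more model degree of freedom than the present fallback, and about 70–75% power against 83% for the F test if the true differences are pure cohort steps.
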